Title: Evaluate the Efficacy of Two Advanced Skin Treatment Regimens in Treating Incontinence-associated Dermatitis: Cluster Randomization Study

Study protocol

Study design

An open-label, cluster randomized, three-group, prospective study will be adopted. Cluster randomization will be used to allocate the selected wards to the experimental or control group for ease of operation (Hemming, Eldridge, Forbes, Weijer, amp; Taljaard, 2017), avoiding confusion on the treatment regimens and cross-contamination of subjects (Sedgwick, 2012). The randomized code for the nursing units will be generated using www.randomizer.org as Treatment 1 or Treatment 2 or Control. Blinding is not possible as the treatment products cannot be “masked”. A purposive sampling on inpatients with IAD will be recruited into the study upon consent. The inclusion and exclusion criteria are as listed in K1 amp; K2. The participants will automatically follow the randomization code selected (implied either control or treatment arm) by the nursing unit he is being admitted.

Study materials

Control

The control regimen for IAD is the current standard of care implemented by the organizations participating in the study. The control regime are combination of treatment - varied practices currently for the treatment of IAD – including the use of potassium permanganate, barrier cream or zinc oxide with skin wipes or soap and water for cleaning

Treatment products

The recommended treatment for IAD should include a structured skin care regimen containing a skin cleanser and a skin protectant. The chemical components recommended as protectants should contain either zinc-based, petrolatum-based, dimethicone-based, or an acrylic polymer. The four preselected products for review are: (1) Conveen easi cleanse and Coloplast Conveen critic barrier (2) 3M No rinse cleanser and 3M Caviton No string Barrier Film (3) 3M No rinse cleaner and 3M Caviton Advanced Skin Protectant(4) Smith and Nephew Moisturizing cleanser and Secura EP cream 30%

Study process

Screening/Recruitment

1. When a potential candidate is identified, the research team members will be activated.
2. Eligible participants from the cluster randomized nursing units will be screened. If they meet the inclusion/exclusion criteria, the PI / co-I will be approached the participants face-to-face.

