3. The study information will be explained to them at their individual bedside cubicles or a quiet corner of the nursing unit for semi-ambulant participants. Time will be given for consideration to the study. All questions asked will be answered. Upon verbal agreement, the consent will be taken using the appropriate ICFs attached.
4. The nurse-in-charge/doctor-in-charge of the patient will be notified of the participant's agreement to the study.

Study day process

5. Arrangement will be made with the nurse-in-charge to synchronize the daily skin assessments with the study assessment to avoid unnecessary exposure.
6. An initial baseline assessment (Day 0) will be conduct on the participant's buttocks, posterior aspect of thigh and perineal region. The subject will be placed on a lateral comfortable position.
7. Observations made will include the amount and extent of denudement, exudate level, redness, signs of infection and the skin condition.
8. A baseline photo will be taken prior treatment.
9. Concealed treatment codes placed in a sealed opaque envelope will be used for randomizing the cluster. Each nursing units will be asked to draw the sealed envelope. With the sealed envelopes contained numbers 1 to 3 where 1 = Standard of care (control), 2 = Treatment regimen 1, 3 = Treatment regime 2. Each draw will determine the allotted treatment for the study site to adopt.
10. The treatment products will be issued to the nurse for application.
11. The treatment regimens will be applied as per manufacturer's recommendation.
12. Patients will be followed up three times a week for a maximum of 21 days, or until the IAD has healed or discharged from the study site.
13. Each review (including baseline assessment), photos will be taken to document the extent of the IAD over the buttocks and/or thighs and/ or perineal region.
14. All assessments will be made using IADS-D and GLOBIAD tool. Permissions to use the assessment tool has been given.
15. On Day 3, 5 and 7, an assessment will be made to the skin appearance if the IAD has not resolved.
16. Patients on treatment regimens will be identified using visual cue - different flower icons. Patients on control regimens will be treated as per hospital policy on data management
17. All collected data will be entered into the CRF.
18. Upon completion of the data collection, the data will be transcribed into EXCEL and validated independently by two different assigned persons.

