19. The validated data in EXCEL will be imported into SPSS and R for data analysis on a later date.

Data collection

Baseline parameters and other outcome measures that will be collected include the pain scores, classification of IAD and healing rates, episodes of incontinence, deterioration to PI or development of other adverse events (Kon et al., 2017) will be collected based on the case record form. Subsequently, 4 more assessments will be made on the participants on the progress of the IAD following treatment(s)/control regimens.

Data Analysis plan

All data will be entered into a Microsoft Office Excel 2013 and independently verified for accuracy of the transcription. The data will then be imported into Statistical Package for the Social Sciences (SPSS) IBM Version 24 and R for analysis and coding. Descriptive analysis including means and standard deviations or medians and interquartile ranges for the numerical variables and frequencies for categorical variables will be used to describe the study sample characteristics. ANOVA will be used to analyse for group differences. The measure of effect (risk difference or mean difference) and a confidence interval or measure of variation will be examined. The intra-cluster correlation coefficient (ICC) will be examined with an ICC of 0.10 used as the acceptable determine for cluster independence during observations (Thomson 2012). Multivariate regression will be used to evaluate the effect of treatment regimens, adjusting for risk factors. A significance level of 0.05 will be used.

We will measure skin characteristics by an independent wound nurse clinician to determine if the photographs reflected any change in skin, size of redness, skin infection or other changes during the follow-up of days 1, 3, 5 and 7 after application of the product. Photographs will be examined to detect any signs of improvement or deterioration in skin condition – redness, maceration of skin and skin erosion (Van de Bussche et al., 2018). A copy of the photograph assessment form is attached. The outcome measures include the pain scores, assessment scores for IAD and healing rates, episodes of incontinence, deterioration to PI or development of other adverse events (Kon et al., 2017).

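### The plan makes the confidence interval for the treatment effect optional, leaves its alternative undefined, and states no ward term in the models that would produce it

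*Combined protocol and SAP*

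**What the plan says.** The design is given under Study design: "An open-label, cluster randomized, three-group, prospective study will be adopted". The randomized units are nursing wards.

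The Data Analysis plan has one sentence on how the treatment effect is to be reported: "The measure of effect (risk difference or mean difference) and a confidence interval or measure of variation will be examined". The other relevant statements in that section are:

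- Descriptive statistics, for sample characteristics: "Descriptive analysis including means and standard deviations or medians and interquartile ranges for the numerical variables and frequencies for categorical variables".
- The group comparison: "ANOVA will be used to analyse for group differences".
- The adjusted analysis: "Multivariate regression will be used to evaluate the effect of treatment regimens, adjusting for risk factors".
- Clustering: "The intra-cluster correlation coefficient (ICC) will be examined with an ICC of 0.10 used as the acceptable determine for cluster independence during observations".
- The error rate: "A significance level of 0.05 will be used".

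No other section requires a confidence interval for a difference between a regimen and control. The confidence level, the sidedness of the test and the meaning of the alternative to the interval are not stated.

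**The concern.** A confidence interval says how precisely a difference between arms is known. A measure of variation may or may not do so. A standard deviation or interquartile range describes the spread between patients. It does not narrow as the sample grows, and it carries no allowance for ward randomization. The sentence treats the two as interchangeable and leaves the choice open until after the data are seen.

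The choice matters most if a comparison is not significant at 0.05. The reader then needs to know whether a useful benefit has been excluded or the data are too imprecise to tell. The supplied text gives no sample size, power or number of wards that would help with that judgement. The missing ward term adds to the problem: even an interval that is reported could be computed as if patients had been randomized individually.

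**Working it through.** The plan has no numerical claim to reproduce, because the supplied text gives no effect size, standard deviation, event rate or sample size. The figures below are illustrations.

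**Inputs**

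- Significance level 0.05, from the Data Analysis plan. Two-sided is an assumption; z = 1.96.
- ICC 0.10, from the Data Analysis plan, where it is the threshold for accepting independence. It is used here only as the largest value that the plan would still treat as acceptable.
- Ward sizes of m = 5, 10 and 20 patients: assumed.
- An observed difference of 0.2 SD, with 20 or 100 patients per arm: assumed.

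**Step 1. The same SD fits very different precision.** Treating patients as independent, the interval is 0.2 ± 1.96 × √(2/n), in SD units.

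- n = 20: 1.96 × √0.10 = 0.62, so −0.42 to 0.82.
- n = 100: 1.96 × √0.02 = 0.28, so −0.08 to 0.48.

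The SD is identical in both cases, so on its own it does not show which applies.

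**Step 2. An interval rebuilt from SD and n is too narrow.** The design effect is 1 + (m − 1) × ICC. The correct interval is √(design effect) times as wide as the naive one. The true coverage of the naive 95% interval is 2Φ(1.96/√(design effect)) − 1.

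| m | Design effect at ICC 0.10 | Width ratio | Coverage of naive 95% interval |
|---|---|---|---|
| 5 | 1 + 4 × 0.10 = 1.4 | 1.18 | about 90% |
| 10 | 1 + 9 × 0.10 = 1.9 | 1.38 | about 85% |
| 20 | 1 + 19 × 0.10 = 2.9 | 1.70 | about 75% |

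With a smaller ICC of 0.01 to 0.05 and the same ward sizes, the width ratio runs from 1.02 to 1.40.

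**Step 3. The two steps together.** With m = 10 (design effect 1.9), the interval at n = 20 becomes 0.2 ± 0.62 × 1.38, or −0.65 to 1.05. At n = 100 it becomes 0.2 ± 0.28 × 1.38, or −0.18 to 0.58.

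**Step 4. The other reading of the phrase.** If the measure of variation is the standard error of the difference, the estimate ± 1.96 × SE gives an approximate 95% interval, and precision is stated. That interval is valid only if the SE itself accounts for ward, which the plan does not say.

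**The case against.** The strongest reply is that the phrase is attached to the effect measure, so the standard error of the difference is a natural reading. The descriptive sentence names standard deviations and interquartile ranges outright, and the change of term may be deliberate. On that reading precision is reported. This stands: the fault is an undefined term that permits a poor choice, and the plan does not prescribe that choice.

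A reader might infer that the 0.05 verdict of the overall test would be the only inference left. The documents do not support this. The regression is a second planned inference on the treatment effect and would normally yield standard errors, although the plan does not commit to reporting them.

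A reader might also infer that a non-significant result could not be interpreted at all. That goes too far. With standard deviations and group sizes a naive interval can be rebuilt. With the ICC and the ward sizes as well, an approximate clustered interval can be had. The plan says only that the ICC will be examined, so these ingredients may or may not be published.

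Finally, the supplied text refers to criteria in sections K1 and K2 that it does not contain, so it may be part of a longer document. No weight should rest on the sample size being absent from the trial's records.

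**Conclusion.** The point holds as a defect of specification. The plan contains no numerical error. It makes the confidence interval optional, does not define the alternative, and states no ward term in either planned model. If a standard deviation or interquartile range is what gets reported, the precision of each regimen-control difference is not stated directly, and a reader's reconstruction from SD and n would be too narrow.

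The size depends on assumptions. For assumed wards of 5 to 20 patients, the correct interval is about 1.2 to 1.7 times as wide as the naive one if the ICC is at the plan's threshold of 0.10, and 1.02 to 1.40 times if the ICC is 0.01 to 0.05. The plan does not predict an ICC of 0.10, and the ward sizes are not in the documents.

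The consequence is weaker interpretation of a non-significant result. The wording alone would be close to a reporting clarification. The missing ward term is what makes the change worth asking for, because it aligns the analysis with the unit that the trial randomizes.

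**What to change.** Replace the choice between an interval and a measure of variation with text such as:

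> Each regimen-control risk difference or mean difference will be reported with its two-sided 95% confidence interval, from a model or cluster-level analysis that accounts for ward, with a small-sample correction if wards are few. Standard deviations or interquartile ranges will be given in addition, as descriptive statistics within each arm.

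The change needs no further patients, visits or data, provided that each patient's ward is recorded in the dataset. SPSS and R, both already named in the plan, can do the analysis. It is more than a change of words, because ward must enter the analysis and the ANOVA and regression as now described do not state that it does. The intervals will be wider than naive ones and may show that the trial is imprecise. The new text does not settle multiplicity across the two comparisons with control, and the plan should say separately whether the intervals are adjusted for it.

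### Wards are randomised, but no analysis accounts for the ward, and an ICC of 0.10 is wrongly accepted as independence between patients

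*Combined protocol and SAP*

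**What the plan says.** Under Study design, the ward is the unit of allocation: "Cluster randomization will be used to allocate the selected wards to the experimental or control group for ease of operation". Patients take the arm of their ward: "The participants will automatically follow the randomization code selected (implied either control or treatment arm) by the nursing unit he is being admitted". Step 9 of the Study day process has each unit draw a code for one of three arms ("Each nursing units will be asked to draw the sealed envelope") and adds: "Each draw will determine the allotted treatment for the study site to adopt". Treatment is therefore constant within a ward.

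The Data Analysis plan states the comparison as "ANOVA will be used to analyse for group differences" and the adjusted analysis as "Multivariate regression will be used to evaluate the effect of treatment regimens, adjusting for risk factors". The level is given by "A significance level of 0.05 will be used". Clustering is mentioned once: the ICC is to be examined, "with an ICC of 0.10 used as the acceptable determine for cluster independence during observations". The plan does not say what follows if the estimate is above or below that value. The documents give no number of wards, no ward size and no expected ICC.

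**The concern.** Patients on one ward share staff, case mix and routine incontinence care, so their outcomes tend to be alike. When wards are randomised, that likeness enters the comparison of arms in full and must enter the standard error too. Neither the ANOVA nor the regression, as described, does this.

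The ICC sentence does not repair the omission. It is a threshold, not an adjustment, and it suggests that patients may be treated as independent when the ICC is about 0.10. The loss depends on the ICC multiplied by the number of patients per ward less one, so no fixed ICC value can be called negligible without knowing ward size.

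At stake is every between-arm test and interval. If patients are the unit, standard errors and p-values are too small and confidence intervals too narrow. An ordinary difference between wards could then be reported as a product effect. The trial is open-label and its control care varies between organisations, so such differences are plausible.

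**Working it through.** The plan has no sample size, power or design-effect figure to reproduce, so the check computes the consequence of the analysis as described.

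**From the documents:** three arms, wards randomised, ANOVA, level 0.05, ICC value 0.10.

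**Assumed:** a continuous, normal outcome; equal ward sizes of m patients; 2 to 6 wards per arm; no true treatment effect.

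**Formulas**
- Variance inflation of an arm mean: DE = 1 + (m − 1) × ICC.
- Understatement of the patient-level standard error: 1 − 1/√DE.
- Actual coverage of a nominal 95% pairwise interval: 2Φ(1.96/√DE) − 1.
- Large-sample rejection rate of the three-group test: P(χ² on 2 df > 5.991/DE).

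For example, with m = 10 and ICC 0.10, DE = 1 + 9 × 0.10 = 1.9. The standard error is too small by 1 − 1/√1.9 = 27.5%, and the rejection rate is P(χ² > 5.991/1.9) = 20.7%.

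The small-sample behaviour was checked by simulation with 2, 3, 4 or 6 wards per arm and 20,000 replicates per setting. The ranges below are over ward counts. Two readings of the ICC sentence were run: (a) ANOVA on patients whatever the ICC; (b) 0.10 as a pre-test, with patient-level ANOVA if the estimate is at or below 0.10 and a ward-level test otherwise.

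True ICC 0.10, nominal 5%:

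| m | DE | SE too small by | 95% interval covers | Rejection, large-sample | Rejection (a), simulated | Rejection (b), simulated |
|---|---|---|---|---|---|---|
| 3 | 1.2 | 8.7% | 92.6% | 8.2% | 8.4–8.5% | 5.1–5.6% |
| 5 | 1.4 | 15.5% | 90.2% | 11.8% | 11.6–12.3% | 7.1–7.7% |
| 10 | 1.9 | 27.5% | 84.5% | 20.7% | 20.9–21.8% | 12.4–13.5% |
| 20 | 2.9 | 41.3% | 75.0% | 35.6% | 36.1–37.2% | 20.5–22.9% |
| 30 | 3.9 | 49.4% | 67.9% | 46.4% | 46.2–47.6% | not run |

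An ICC below the threshold still matters under (a). For m = 5, 10 and 20 the rejection rate is about 8%, 13% and 22% at ICC 0.05, and about 6%, 8% and 11% at ICC 0.02.

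An ANOVA on ward means stayed between 4.6% and 5.4% in every setting with at least two wards per arm. Its error degrees of freedom are wards minus arms: 3 × 2 − 3 = 3 with two wards per arm, 3 × 6 − 3 = 15 with six, and 3 × 1 − 3 = 0 with one.

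**The case against.** The plan never states that patients are analysed as if independent. ANOVA on ward means would be valid, and by examining the ICC the plan shows awareness of clustering. This stands as far as it goes: the claim about standard errors is conditional on a patient-level reading. That reading is still the natural one. A ward-mean analysis needs no check of independence, and a regression on risk factors is normally fitted to patients. Examining an ICC changes no standard error.

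Both readings of the 0.10 sentence are constructions, since the sentence attaches no action to the value. That is true, and it is why both were computed. The pre-test is less harmful than ignoring the ward: it is close to nominal at 3 patients per ward, and at ICC 0.02–0.05 it gives about 4–5% at m = 3 and 5–7% at m = 5. It rises to about 7–11% at m = 10 and 10–20% at m = 20. With a true ICC of 0.10 the estimate falls at or below 0.10 in 52–61% of trials. This is weak evidence on its own, because an estimate is expected to fall below its true value about half the time. The stronger point is that a value at or below 0.10 does not justify ignoring the ward.

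All rates depend on assumed ward numbers, sizes and ICC, and on a normal outcome; healing and deterioration to pressure injury were not simulated. One ward per arm is only not excluded: the numbers 1 to 3 are arm codes, not a count of wards. These limits bear on the size of the error. They do not touch the missing ward-level method or the invalid threshold.

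**Conclusion.** The concern holds. Two things are certain from the text: no analysis that accounts for the randomised unit is specified, and the one stated rule on clustering treats a non-negligible ICC as independence. If patients are the unit of analysis, the error runs in one direction for any positive ICC once wards contribute more than one patient.

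Its size cannot be fixed from the documents. Over the settings examined, the true error rate of a nominal 5% test that ignores the ward runs from about 6% (ICC 0.02, 5 patients per ward) to about 48% (ICC 0.10, 30 patients per ward). This must be corrected before analysis, because it bears on every comparison between arms.

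**What to change.** - Delete the 0.10 rule. Report the ICC with its confidence interval as description only.
- State the number of wards per arm and the expected patients per ward. Settle whether the randomised unit is the ward or the study site, since step 9 of the Study day process refers to both, and use that unit as the cluster.
- Account for the cluster in every between-arm comparison, including the risk-factor regression, whatever the ICC estimate. For scores, a linear mixed model with a ward random effect and small-sample degrees of freedom would serve. For yes/no outcomes such as healing or deterioration to pressure injury, use GEE with a small-sample correction or ward-level summaries on wards-minus-arms degrees of freedom.
- With very few wards per arm, use ward-level summaries. Fix in advance the ward count below which this applies.
- If there is one ward per arm, state that treatment cannot be separated from ward and report the results as descriptive, or add wards.

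With at least two wards per arm this needs new wording only; R is already named as software. The price is wider intervals and fewer nominally significant results. With two wards per arm, 3 error degrees of freedom may leave the trial uninformative, which is a limit of the design that wording cannot remove.

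### Six unranked outcome types share one 0.05 level, with no primary endpoint, time point, contrast with control or multiplicity rule, so the familywise error is uncontrolled

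*Combined protocol and SAP*

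**What the plan says.** The Study design section sets the structure: "An open-label, cluster randomized, three-group, prospective study will be adopted". The groups are two treatment regimens and standard care, and the title asks about the efficacy of both regimens.

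The Data Analysis plan gives the outcomes in one sentence: "The outcome measures include the pain scores, assessment scores for IAD and healing rates, episodes of incontinence, deterioration to PI"; its last item is any further adverse event. Neither this list nor the similar one under Data collection marks any item as primary or secondary. Item 14 of the Study day process adds that IAD is assessed on two tools, IADS-D and GLOBIAD.

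Timing is described in several ways, and none is tied to the main analysis:
- Study day process, item 12: "Patients will be followed up three times a week for a maximum of 21 days", ending earlier on healing or discharge.
- Study day process, item 15: Days 3, 5 and 7, if the IAD has not resolved.
- Data collection: "Subsequently, 4 more assessments will be made on the participants on the progress of the IAD following treatment(s)/control regimens".
- Data Analysis plan, for the photographs: "during the follow-up of days 1, 3, 5 and 7 after application of the product".

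On testing, the Data Analysis plan says "ANOVA will be used to analyse for group differences". It adds a risk or mean difference with a confidence interval or measure of variation, and a multivariate regression for the effect of the regimens adjusted for risk factors. The error rule is "A significance level of 0.05 will be used". No sidedness, adjustment, test order, reference group or pairwise contrast is given.

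**The concern.** With no primary endpoint and no fixed time, the plan does not define in advance what result would count as success. Following it as written, the investigators could base an efficacy claim on any listed outcome that reached 0.05. The trial is open-label, so a choice of outcome or day made after the data are seen would be hard to defend.

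The three-group structure adds a second gap. A significant ANOVA says that the groups differ somewhere; it does not say which regimen, if either, does better than standard care. The planned effect measures and regression could answer that, but the plan does not say which comparison they will make or on which outcome.

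**Working it through.** The plan has no derived error rate, sample size or power figure to reproduce. The one stated figure is 0.05. The question is what overall error follows from it.

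**Inputs from the documents**
- Level 0.05 (Data Analysis plan), taken here as two-sided because sidedness is not stated.
- Three groups (Study design).
- Six outcome types by count (Data Analysis plan): pain scores, IAD scores, healing, episodes of incontinence, progression to PI, and other adverse events.
- Four post-baseline assessments (Data collection).

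**Assumptions.** No true effect on any outcome; the number of tests; the correlation between tests; three equal groups and large-sample normality in the simulations. Clustering is ignored.

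**Step 1. One test per outcome.** If k tests are independent, the chance of at least one false positive is 1 − 0.95^k. For k = 6 this is 1 − 0.735 = 0.265.

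Listed outcomes are likely to be correlated, which lowers the figure. Simulation with equally correlated normal test statistics gives 0.207 at correlation 0.5 and 0.166 at 0.7. A second simulation, using the three-group omnibus test itself, gives 0.246, 0.213 and 0.169 at between-outcome correlations of 0.3, 0.5 and 0.7. The two approaches agree closely at 0.5 and 0.7.

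**Step 2. Each regimen against control, one outcome at one time.** Two independent tests would give 1 − 0.95² = 0.0975. Sharing one control group makes the two tests correlated; simulation gives 0.089 to 0.092. In the direction of benefit only, it gives 0.045.

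**Step 3. Six outcomes, each with two comparisons against control.** Twelve independent tests give 1 − 0.95^12 = 0.460. With the shared control the simulated figure is 0.432, and with correlated outcomes 0.282 to 0.401. In the direction of benefit only, the range is 0.143 to 0.245.

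**Step 4. Scenario only: six outcomes at each of four visits.** For 6 × 4 = 24 independent tests, 1 − 0.95^24 = 0.708. At equal correlations of 0.5 and 0.7 the figures are 0.457 and 0.312. The plan does not state that this grid will be tested.

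**Step 5. After naming one endpoint at one time.** Only the two contrasts remain. Holm tests the smaller p-value at 0.05 / 2 = 0.025 and, if that is significant, the other at 0.05. The familywise error is then at most 0.05, provided each test is valid for ward-randomized data. If no endpoint were chosen, Bonferroni would need 0.05 / 6 = 0.0083 per test for six tests and 0.05 / 12 = 0.0042 for twelve.

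**The case against.** A reader might infer three stronger things, and the documents support none of them.

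First, that ANOVA is the only test, so that neither regimen is ever compared with control. The Data Analysis plan also names risk or mean differences and a regression for the effect of the regimens. With control as the reference group, that regression would give each regimen its own coefficient and test. The gap is that the outcome, the reference group and the pair of groups are unspecified.

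Second, that every outcome is tested at every visit. The plan says no such thing. The listed photograph days concern skin change, the four further assessments concern progress of the IAD, and healing, PI and adverse events could each be analysed once per patient.

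Third, that a false claim of benefit is likely. The figures for six tests stay below 27% and count errors in either direction; episodes of incontinence and adverse events may not be efficacy outcomes at all. The count of six is itself soft: joining the paired items gives four, and 1 − 0.95^4 = 0.185.

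It can also be said that, with three groups, making pairwise tests only after a significant ANOVA protects them within one outcome at one visit. That is correct, but the plan does not state such a sequence, and it would not protect across outcomes.

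Finally, the eligibility sections that the protocol cites (K1 and K2) are not in the supplied text, so any statement about what is absent is limited to that text. What survives is that the supplied plan ranks no outcome and controls no familywise error.

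**Conclusion.** The point holds as a cheap improvement. The supplied plan leaves open the primary endpoint, its time point, the contrasts with control and the handling of multiplicity, and offers only an unqualified 0.05.

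The headline size is 17% to 26% for at least one false positive in either direction. It rests on one test per outcome, six outcomes, no true effects, and correlations from 0.7 down to zero. On a four-item reading, the independent figure is 18.5%. The range of 31% to 71% would apply only if all six outcomes were also tested at each of four visits. About 9% applies even to one outcome at one time if both regimens are compared with control without adjustment or a preceding omnibus test.

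These figures assume valid individual tests. Wards are randomized, so an ANOVA that treats patients as independent would raise the error further.

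**What to change.** Before the data are analysed, add the following to the Data Analysis plan:

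1. **One primary endpoint at one time.** For example, IADS-D at Day 7, which is the last visit named in both the Study day process and the Data Analysis plan. Healing or the other IAD tool could be chosen instead; what matters is that the choice is made in advance.
2. **Rules for patients not assessed at that time.** Keep healed patients at the healed score. State how patients discharged unhealed before then are handled, for example by a mixed model that uses all their available scores, with its missing-data assumption stated.
3. **Two planned contrasts as the primary analysis.** Regimen 1 against control and regimen 2 against control, from a model that accounts for ward clustering, with Holm or an equivalent adjustment for an overall two-sided 0.05. Adjusting patient-level tests that ignore wards would not hold that level.
4. **All other outcomes and visits as secondary.** Report estimates and confidence intervals, with no confirmatory efficacy claim.

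The change is to the analysis text; the example endpoint needs no new data. The costs are that each primary contrast is tested more strictly (0.025 at the first Holm step) and that secondary outcomes can no longer carry the conclusion. The loss of power cannot be computed, because the supplied text gives no sample size or number of wards.
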